Annex 2. Genetic information (examples)

Information related to genetic sequencing can be included in the epidemiological database, or provided separately in a spreadsheet, as below. The minimum amount of data needed to obtain genetic data from GISAID (sequences of all viruses should be sent to GISAID's open access EpiCoV platform) is ID number and GISAID accession number. Additional information on CT value, selection for characterisation, and reasons for not characterising can be additionally collected (see Table A2).

Table A2. Example of a data collection form for genetic data

[figure not shown]
	Unique ID number	GISAID accession ID number	Selected for characterisation?	Reasons for not characterising?	CT value	Type of sample (primary specimen or isolate)
Strain 1						
Strain 2						

Where not all viruses were attempted to be sequenced, but only a random selection of them, additional information on sampling fraction should be provided. An example can be seen in Table A3.

Table A3. Example of documenting how viruses were selected for sequencing over time

Time period	First date of time period	Last date of time period	Sampling fraction used	Date used for definition of time unit (onset date, swab date, other)	Comments
Example1	01/10/2020	31/12/2020	1	Date of onset	(this is only an example; all specimens were characterised)
Example2	01/01/2021	15/02/2021	0.2	Date of onset	(this is only an example; 20% of all specimens were characterised)

Annex 3. Data flow for pooled dataset

Annex 4. Detailed pooled analysis plan

Each individual study site can analyse their data. Example scripts can be provided if desired, and support is available for analysis. The following analysis plan covers the pooled analysis.

Descriptive analysis

The proportion of eligible hospitalised cases and controls who accepted to participate in the study will be calculated. The proportion of patients not consenting will be documented, along with reasons for no participation. Patients excluded will be described in a study flowchart.

Cases and controls will be described by baseline characteristics (Table A4).

The main characteristics of each study will be summarised individually, including:

- number of GPs/GP centres participating and catchment population;
- beginning of vaccination campaigns for COVID-19 and for influenza vaccines;
- definitions of target groups for vaccination;
- beginning and end of the study period;
- vaccine product(s) used; and
- estimated vaccine coverage in the country/region by vaccine brand, by target vaccine group.

Table A4. Example for CVE (or IVE) of descriptive table for cases and controls

Variables	Number of laboratory-confirmed COVID-19 (or influenza) cases/total n (%)	Number of test-negative controls/total n (%)
Median age (IQR)	X	X
Missing	X	X
Age groups (years)		
0–14	x/x (x)	x/x (x)
15–44	x/x (x)	x/x (x)
45–64	x/x (x)	x/x (x)
65–79	x/x (x)	x/x (x)
≥80	x/x (x)	x/x (x)
Missing	X	X
Sex		
Female	x/x (x)	x/x (x)
Missing	X	X
Days between onset of symptoms and swabbing		
0	x/x (x)	x/x (x)
1	x/x (x)	x/x (x)
2	x/x (x)	x/x (x)
3	x/x (x)	x/x (x)
4–7	x/x (x)	x/x (x)
8–10 (if CVE)	x/x (x)	x/x (x)
COVID-19/influenza vaccination status	x/x (x)	x/x (x)
Missing	x	X
Etc.		

Patients will be described according to:

- sex;
- age group;
- healthcare worker status;
- time: month of symptom onset;
- symptoms;
- high-risk condition: absence, presence of at least one, presence of more than one
- specific chronic conditions (e.g. respiratory, cardiovascular diseases);
- pregnancy;
- COVID-19 and influenza vaccination status;
- respiratory co-infections; and
- study site.

Measure of effect

This study is a case control study (test-negative design). The measure of association is an odds ratio (OR). This can be measured by logistic regression. An OR = 1 indicates no association between an exposure and the outcome. An OR > 1 indicates a potential risk factor, an OR < 1 indicates a potential protective factor, noting that the confidence interval around the OR helps with its interpretation.

For vaccination as preventive factor, the VE can be computed as $VE = (1 - OR) * 100$. A 95% confidence interval is computed around the point estimate.

Pooled crude VE estimates

We will estimate crude VE, adjusting for study site as a fixed effect and adjusting for symptom onset time. We will adjust for study site, as this is part of the multicentre study design, and for calendar time, as this is an integral part of the test-negative design.

The primary analysis for the pooled VE estimates will be a one-stage approach, where individual data from study sites are pooled and study site is included as a fixed effect covariate in the model. The one-stage analysis is useful approach, particularly if smaller study sites are included and it can provide good modelling flexibility. Study site can be included as a fixed effect or if enough study sites are available potentially as a random effect in a multilevel model. The fixed effect assumes the same VE for all study sites, with differences due to random variation, rather than to essential differences in VE.

Statistical heterogeneity between study sites will be determined, using Q-test and the I2 index [28] and a two-stage pooled analysis approach can be carried out in a sensitivity analysis.

Pooled stratified analysis

The analysis can be stratified according to (if sample size allows):

- age groups (e.g. <20, 20-44, 45-64, 65+ years);
- sex;
- presence of at least one chronic condition, or specific chronic conditions; and
- calendar time and time since vaccination.

A sufficient sample size should be planned in order to ensure enough people in each stratum for a precise estimate. Effect modification should be assessed comparing the VE across the strata of the baseline characteristics. Confounding should be assessed by comparing crude and adjusted VE for each baseline characteristic.

Pooled multivariable analysis

A multivariable logistic regression analysis will be conducted to estimate VE and control for negative and positive confounding. Odds ratios and standard errors will be obtained. Variables will be tested for multicollinearity. Interactions will be tested using the likelihood ratio test or Wald's test and will be included in the model if significant at the 5% level. Factors other than statistical significance (prevalence of exposure, magnitude of OR/VE, biological plausibility) will also be used as criteria for inclusion of a variable or an interaction term. As noted in the 'Pooled crude VE estimates' section, study site and onset time should always be controlled for in each model.

Variable selection and model specification

Model development strategy

To find a suitable model, we will consider very carefully the variables collected and determine which are GP level variables, which are individual level variables, which variables are mediators of each other, and which variables are

potential confounders and effect modifiers. Variables will also be checked for collinearity, and decisions will be made to include the group of collinear variables in the model or select among them.

The above considerations are particularly important for this study, as some of the medication information collected and the chronic conditions of the patients may be strongly correlated.

Creating a direct acyclical graph may help better understand the relation between all variables collected and the outcomes.

Some variables will be a priori variables. These are variables that we want to keep in the model, as previous studies have shown them to be potential confounders or effect modifiers. These could include age and sex, but also potentially others.

If the model is not overfitted and variables are included that are not collinear or mediators, then there may be less concern for parsimony, as including insignificant variables may result in more accurate p -values for tests for variables of interest.

However, if sample size is low and the model is overfitted, then a backwards step-down variable selection procedure could be considered.

Interaction terms should be included cautiously, factors other than statistical significance (prevalence of exposure, magnitude of OR) will also be used as criteria for inclusion of an interaction term.

Several different models may have to be presented and considered.

Continuous variables

Continuous variables in the data include age, date of onset of symptoms, and number of GP visits and hospitalisations. These variables can be coded as categories, e.g. age group, week of symptom onset, etc. However, when coding continuous variables as categories, you may lose information, introduce residual confounding and increase the standard error of your model. Tests will be carried out to see if these variables could be coded as a linear term, polynomial or a spline. In addition, a balance will be sought between model simplicity (so a non-expert can understand what is going on), precision and bias minimisation.

Output tables presenting VE

In order to present the results in the most transparent manner and to enable the reader to best understand the data, tables similar to the one illustrated by Table A5 can be used (variables presented just as an example of the output format). Useful information includes numbers of cases and controls and presentation of results for different models.

Table A5. Example table of VE for COVID-19 (or influenza), primary care-based VE study

Clade/variant	Population included	Analysis scenarios/adjustments made	CVE (or IVE) (%)	(95%CI)
COVID-19 (or influenza)	All ages	N (cases/vaccinated; controls/vaccinated)		
		Crude*		
		Adjusted for onset date (cubic spline)		
		Adjusted for sex		
		Adjusted for chronic condition		
		Adjusted for age (cubic spline)		
		Adjusted for onset date, age (cubic spline)		
		Adjusted for onset date, chronic condition		
		Adjusted for onset date, age (cubic spline), chronic conditions, sex		
		0–49 years	N (cases/vaccinated; controls/vaccinated)	
	Crude*			
	Adjusted for onset month, age (cubic spline)			
50 years and over	N (cases/vaccinated; controls/vaccinated)			
	Crude*			
	Adjusted for onset date, age (cubic spline), chronic condition, sex			

* Symptom onset time and study site is always included in the model.

Minimum sample size

Sample sizes may be very small for some sub-analyses. Different criteria can be used to determine whether the sample size is large enough to obtain a valid measure of odds:

- There are at least 10–15 cases (or controls, whichever is smaller) per study site in the sub-analysis for crude analyses and more for adjusted analyses (e.g. at least 10 for each parameter in the model);
- There are ≥ 5 records in each cell of the two-by-two table of case and exposure status.

With low sample size, we should consider collapsing categories, modelling continuous variables in a different way (if applicable). Sensitivity analyses can be carried out using penalised logistic regression.

Controlling for GP effect

Primary analyses will be carried out using standard logistic regression to obtain the individual study VE estimates. However, there could be variability between GPs. To adjust for this possible cluster effect, a multi-level logistic regression with each GP as a random effect will be carried out and compared to the single level analysis.

The same applies to stratified analyses. The point estimates and confidence intervals from the multi-level and simple logistic regression will be compared in a sensitivity analysis.

Identifying heterogeneity, testing for heterogeneity

Country-specific crude and adjusted VE and their confidence intervals will be plotted in separate forest plots. Following the core protocol minimises heterogeneity between studies. However, adherence to the protocol and study design and study quality characteristics will also be checked. Other study site characteristics will be assessed where feasible, such as types of circulating virus, information on healthcare use, and organisation of the vaccination campaign. Then a qualitative decision will be taken if one or more studies are substantially different from the other and should be excluded from the pooled analysis.

Statistical heterogeneity between studies will be tested using Q-test and the I^2 index (see boxes for formulae below). The Q statistic follows a χ^2 distribution (with $k-1$ degrees of freedom). The Q-test reports presence or absence of heterogeneity, while the I^2 index (based on the Q-statistic) quantifies the extent of the heterogeneity. According to the Higgins and Thompson classification, an I^2 index of around 25% indicates low, 50% indicates medium and 75% indicates high heterogeneity between studies [29].

$$Q = \sum w_i (\log(OR_i) - \log(OR_F))^2$$

Where:

$$w_i = 1 / v_i$$

v_i is the inverse variance of the estimated log odds ratio of study i

$$\log(OR_F) = \frac{\sum w_i \times \log(OR_i)}{\sum w_i}$$

$$I^2 = \frac{Q - (k - 1)}{Q} \times 100\% \quad \text{for } Q > (k - 1)$$

$$I^2 = 0 \quad \text{for } Q \leq (k - 1)$$

Formulae are given here for completeness; in practice these measures are automatically calculated by many statistical software packages as part of the meta-analysis commands.

Two-stage pooled analysis approach

A one-stage pooled analysis approach is the primary analysis, and a two-stage meta-analysis approach can be used to obtain the pooled VE estimate in a sensitivity analysis. Study-specific adjusted ORs and standard errors for the effect of different vaccination definitions obtained from the individual studies, will be combined in a model that incorporates random effects of the studies, to account for unmeasured country- and study-specific factors that differ between studies. In a random effects model, the study site-specific estimates are assumed to be normally distributed around a central effect. Thus they are allowed (expected) to differ from each other.

The study-specific exposure-disease effects are then weighted by the inverse of their marginal variances. The marginal variance is the sum of the individual study-specific variances and the variance of the random study effects (τ^2). This will give the pooled odds ratio and standard error (using the DerSimonian Laird approach).

$$\log(OR_R) = \frac{\sum w_i^* \times \log(OR_i)}{\sum w_i^*}$$
$$w_i^* = \frac{1}{v_i + \tau^2}$$

In the sensitivity analysis, the two-stage approach can be compared to a one-stage pooled analysis approach, where individual study data are combined and study site is added as a fixed effect (for example).

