5.1 Potential biases

5.1.1 Bias from pooled estimates

With data from study sites from different countries being pooled, any bias in the individual studies will influence the pooled estimate. The power of the test for the presence of heterogeneity between individual studies is low if there are few sites/countries. In this case, the test may not be able to detect heterogeneity between them, despite it being present. It is important that heterogeneity is also assessed using qualitative knowledge about differences between studies. Depending on the nature of the bias, the inclusion of biased studies in the pooled estimate could lead to over- or underestimation of the true association between influenza/COVID-19 vaccination and the outcome.

There are many conditions which could lead to bias in a study site. For CVE, being a novel virus, there are evolving surveillance systems and strategies in each participating country. There are different tests being used (PCR and rapid antigen tests), potentially for different age groups and with changes over time, which may impact how the SARS-CoV-2 outcome is defined (particularly if rapid antigen tests are used for defining the SARS-CoV-2 outcome). Additionally, home testing may affect who sees a GP for an ARI or ILI episode, as knowing their SARS-CoV-2 status may affect whether people consult their GP (which may be differential by vaccination status).

To allow for complete assessment of heterogeneity, study sites need to document all changes in their influenza and COVID-19 surveillance system/s during the study period.

- *Each country to document any changes in influenza/COVID-19 surveillance during the study period.*

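### Annex 4 decides which sites leave the pooled analysis after country-specific VE has been plotted, with no criterion that keeps the decision apart from the results and no promised all-site estimate

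*Protocol*

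**What the plan says.** The rule is in Annex 4 of the protocol, under the heading on identifying and testing for heterogeneity. It runs in this order:

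1. "Country-specific crude and adjusted VE and their confidence intervals will be plotted in separate forest plots".
2. The text then says that "adherence to the protocol and study design and study quality characteristics will also be checked". Other site characteristics are assessed where feasible, "such as types of circulating virus, information on healthcare use, and organisation of the vaccination campaign".
3. The exclusion step comes next: "a qualitative decision will be taken if one or more studies are substantially different from the other and should be excluded". What the site would leave is the pooled analysis.
4. The Q-test and I² are described in the next paragraph.

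Section 5.1.1 gives the background. The heterogeneity test has little power when sites are few, so "It is important that heterogeneity is also assessed using qualitative knowledge about differences between studies". That section sets no rule for removing a site.

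The primary pooled analysis is one-stage: "individual data from study sites are pooled and study site is included as a fixed effect covariate in the model". Annex 4 adds that "The fixed effect assumes the same VE for all study sites, with differences due to random variation". A two-stage random-effects analysis is an optional sensitivity analysis. It changes the model, not the set of sites.

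**The concern.** The people deciding which sites stay have the country-specific VE in front of them. The protocol does not define what counts as substantially different, who decides, or whether the plotted VE may play a part.

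The listed grounds also mix two kinds of difference. Poor adherence or a design fault is a reason to distrust a site. Circulating virus, healthcare use and campaign organisation are real features of a site, and removing a site for them changes the population that the pooled VE describes.

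Q and I² come after the exclusion step, and the text does not say that they use all sites. They may therefore be calculated after a source of heterogeneity has gone.

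Pooled VE is part of the primary objective (section 2.1), and section 3.13.3 plans interim pooled analyses, so the decision may recur. If a site goes because its VE looks odd, the pooled VE can shift, and the reported interval takes no account of the selection.

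**Working it through.** **Scale check against the protocol.** The documents give no figure for the exclusion rule. Table 4 does fix the variance of a log OR, for *n* cases and *n* controls:

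n = [1/(p₁q₁) + 1/(p₀q₀)] × [1.96 / ln((OR + precision)/OR)]²

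For OR 0.5, 50% coverage and precision 0.2: p₀ = 0.5 and p₁ = 1/3, so the first bracket is 4.5 + 4 = 8.5. The second is (1.96/ln 1.4)² = (1.96/0.3365)² ≈ 33.9. The product is 288.4, rounded up to 289, as in Table 4.

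**Assumptions that are not in the documents.** Ten equal sites; SE of each site's log OR 0.35 (at OR 0.5 and 50% coverage, 8.5/0.35² ≈ 69 cases and 69 controls per site); true VE 50%; between-site SD of the log OR (τ) 0 or 0.35; exactly one site always dropped. With equal sites, the inverse-variance pooled log OR is the plain mean. It stands in for the one-stage model with a fixed site term.

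**Bias when the lowest-VE site is dropped, τ = 0.** The largest of ten standard normal values has expectation about 1.539. Removing it shifts the mean of the other nine by −1.539 × 0.35/9 ≈ −0.060. Then OR = 0.5 × e^(−0.060) ≈ 0.471 and VE ≈ 52.9%. Simulation agrees (shift −0.0595).

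**Coverage of the nominal 95% interval.**

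| Rule | τ = 0 | τ = 0.35 |
|---|---|---|
| All ten sites | 95% | about 83% |
| One site dropped regardless of VE | 95% | about 83% |
| Most extreme site dropped | about 92% | about 77.5% |

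The 83% needs no simulation. The reported SE is 0.35/√10 = 0.111, while the true SD is √(0.35² + 0.35²)/√10 = 0.157. The ratio is 0.707, and 2Φ(1.96 × 0.707) − 1 ≈ 0.834. That shortfall comes from the common-VE model, not from exclusion. Exclusion accounts for the further fall to about 77.5%. Mean I² falls from about 41% to about 22%.

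**What too narrow means.** Dropping a site widens the interval in absolute terms: the reported SE rises from 0.111 to 0.35/√9 = 0.117. With τ = 0 and the most extreme site dropped, the true SD is about 0.132. The interval is narrow only relative to that.

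**Sensitivity to the assumptions.** With 150 cases and 150 controls per site, the SE is √(8.5/150) = 0.238. The figures below are fixed-effect coverage.

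- Most extreme site always dropped, τ = 0: 91.1% (5 sites), 91.5% (8), 92.1% (12).
- Same rule, 5 sites, τ = 0.2: 80.2%, against 86.6% with all sites.
- Drop only sites whose interval excludes the pooled value: 93.2% to 93.7% with τ = 0; about 84% against about 87% with τ = 0.2; no loss with τ = 0.4 (69.1% to 70.1%, against 68.3% with all sites).
- Lowest-VE site always dropped, 5 sites: pooled VE 53.3% with τ = 0, rising to 56.3% with τ = 0.4.
- One site dropped regardless of VE, τ = 0: 94.9% to 95.1%.

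**The case against.** The strongest reply is that the decision follows directly on the checks of adherence, design, quality and context, and that it concerns studies rather than estimates. Read with section 5.1.1, the word qualitative points to judgement about how the sites were run. This stands. A reader might infer from the order of steps that the results choose the sites. The protocol does not say so: every ground it names is a non-result ground.

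A reader might also infer that the pooled interval is always too narrow. That does not follow. Exclusion unrelated to VE costs no coverage, and the size of any loss depends on rules and inputs that the protocol does not state. The illustration always drops a site, whereas the protocol excludes only if a site is judged substantially different.

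Nor does the protocol say that the all-site estimate is discarded; it is silent. Country-specific VE is to be plotted, and section 3.13.3 has the central hub document and share its data cleaning and analysis with the study coordinators, so differences between sites and exclusions should be traceable within the network.

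Finally, exclusion cannot in general be settled before any site VE exists. Site VE is itself a primary objective, sites may analyse their own data, and interim pooled analyses are planned. That limits what the fix can ask.

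It could be said that exclusion criteria belong in a separate analysis plan. This carries less weight, because Annex 4 is the detailed pooled analysis plan and does fix a sequence. None of these replies supplies a step that keeps the plotted VE out of the decision, or a commitment to show the all-site result.

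**Conclusion.** The point holds in conditional form. Annex 4 sets an order in which site VE is visible when sites are excluded, gives no criterion that separates the decision from VE, allows exclusion for real differences between sites, and promises no all-site estimate. If exclusion follows the plots, it can bias the pooled VE and understate its uncertainty.

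Under the ten-site assumptions the effect is about 3 points of VE when the lowest-VE site is dropped. When the most extreme site is dropped, it is about 3 points of coverage with a common VE and about 6 points with between-site SD 0.35. Milder rules mostly lose less. The number and size of sites, τ and the dropping rule are all assumed, so these figures show scale and do not predict what will happen. The change is worth making because the rule is fixed in the wrong order and is cheap to put right.

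**What to change.** In the heterogeneity part of Annex 4:

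- Move the check of adherence, design and quality ahead of the forest plots.
- Have the central hub record any exclusion from the pooled analysis, on written design and quality criteria, before it compares site VE for that analysis. This can be done even where sites have already estimated their own VE.
- Always report the all-site pooled VE, Q and I² beside any reduced set.
- Use the forest plots only for leave-one-site-out sensitivity analyses.

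The cost is new annex wording, a short list of criteria and slightly more reporting. No new data are needed. The network gives up some freedom to drop a site once the plots have been seen.
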